**Appendix L: Survival Form**

**Instructions:** Fill this form out at protocol indicated survival assessments

1. Last known Survival Status:  
 Alive  
 Dead  
 Lost to Follow-up: Date of last contact \_\_\_\_/\_\_\_\_/\_\_\_\_ (MM/DD/YYYY)
2. Expired Date \_\_\_\_/\_\_\_\_/\_\_\_\_ (MM/DD/YYYY)  
Is this an approximate date?  Yes  No
3. Last known Alive Date \_\_\_\_/\_\_\_\_/\_\_\_\_ (MM/DD/YYYY)
4. Survival Status source: \_\_\_\_\_  
*Instructions: Source can be EMR, obituary, family member etc. Phone call with patient  
Add to comments in WISER follow-up section*
5. Comment: \_\_\_\_\_

**Appendix M: Study Withdrawal**

PID Number _____	DOB _____
1. Date Study Treatment Stopped or Withdrawal _____/____/____ (MM/DD/YYYY)	
2. Please check ONE of the following:  Patient did not complete radiation therapy  Patient withdrew or discontinued early	
3. If withdrawn or discontinued early, indicate ONE primary below:  Patient registered but not treated: Specify reason: _____  Radiotherapy attempted, but not completed  Progression during treatment  Unanticipated Adverse Event/Serious Adverse Event  Patient Died: Date of Death ____/____/____ (MM/DD/YYYY)  Unknown date Specify Cause of Death: _____  Unknown cause  Lost to follow-up: Date of Last Contact ____/____/____ (MM/DD/YYYY)  Unknown : Date Last Known to be Alive ____/____/____ (MM/DD/YYYY)  Patient no longer willing to participate in study	

A Randomized Trial of Consolidative Immunotherapy with vs without Thoracic Radiotherapy and / or Stereotactic Body Radiation Therapy (SBRT) after First-line Systemic Therapy for Metastatic NSCLC  
Wake Forest Baptist Comprehensive Cancer Center  
WFBCCC # 62718

**Appendix O: Off-Study Form**

Study Number: \_\_\_\_\_ PID: \_\_\_\_\_

Investigator: [name] M.D. Date \_\_\_\_/\_\_\_\_/\_\_\_\_ (MM/DD/YYYY)

**Instructions:** Complete this form if the patient has completed or is removed from the study.

Name of Person Completing form \_\_\_\_\_

Off study date \_\_\_\_/\_\_\_\_/\_\_\_\_ (MM/DD/YYYY)

Reason:

Adverse Event/Side Effects/Complications;

Death; (if death fill out Survival Form)

Enrolling Physician Decision;

Other;

Patient lost to follow-up; Date of last contact \_\_\_\_/\_\_\_\_/\_\_\_\_ (MM/DD/YYYY)

Patient refused follow-up;

Protocol-defined follow-up completed

Explain \_\_\_\_\_

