**If randomized to consolidative radiation therapy then maintenance immunotherapy:**

Maintenance immunotherapy may NOT be delivered concurrently with consolidative radiation. Concurrently is defined as on the same day of any radiation treatment or on any day between the first and last treatment of radiation. Resumption of maintenance immunotherapy after completion of radiation therapy is at the discretion of the treating medical oncologist. They may resume maintenance immunotherapy as early as 24 hrs after the last radiation treatment, but resumption should be no later than 8 weeks from the last radiation treatment. If treatment related toxicities prohibit administration of maintenance immunotherapy, then restarting this therapy is at the discretion of the treating medical oncologist. In such cases, patients will remain on study until they experience progression or death. If they experience progression, patients will be followed for overall survival only per appendix L past the point of progression.

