#### **8.5 Duration of Therapy**

In the absence of treatment delays due to adverse events, treatment may continue for until one of the following criteria applies:

- Disease progression
- Intercurrent illness that prevents further administration of treatment,
- Unacceptable adverse event(s),
- Patient decides to withdraw from the study, or
- General or specific changes in the patient's condition render the patient Unacceptable for further treatment in the judgment of the investigator.

If a patient is unable to complete a total of 2 years of maintenance Immunotherapy due to toxicity, declining therapy, or intercurrent illness, or any other reason, they will continued to be followed on study until a progression event, death, or withdrawal from study.

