**Appendix F: 30-day Treatment Follow-up Form**

Definition of 1 mo. or 30 day followup

1. For patients randomized to RT, this time point is considered 30 days +/- 14 days from end of all radiation therapy treatments
2. For patients randomized to immunotherapy alone, this time point is considered 30 days +/- 14 days from the end of the 2nd cycle of on protocol maintenance immunotherapy

Study Number: \_\_\_\_\_ PID: \_\_\_\_\_

Investigator: [name] M.D. Date: \_\_\_\_ / \_\_\_\_ / \_\_\_\_ (MM/DD/YYYY)

**Instructions:** Complete this form to follow-up with patients for adverse events.

**Name of Person Competing form** \_\_\_\_\_

**Did the subject have any adverse events in the last 30 days?** Yes  No

If yes, please report on AE log in WISER

(Note\*: If an SAE occurs in this period, report the event as required in Appendix S):

**Was the subject removed from the study?** Yes  No

If yes, complete the Off-Study Form

**Did the subject withdraw from the study?** Yes  No

If Yes, complete the Withdrawal of Consent Form

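### Appendices O and M let toxicity, physician decision or incomplete radiotherapy be recorded as leaving the study, against the follow-up rule in Sections 3.0 and 8.5, so PFS follow-up could end early and unevenly by arm

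*Combined protocol and SAP*

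**What the plan says.** **Body of the protocol.** Section 3.0, under the radiation arm, deals with toxicity that prevents maintenance immunotherapy: "In such cases, patients will remain on study until they experience progression or death". Section 8.5 is wider. For a patient who does not complete two years of immunotherapy because of toxicity, refusal, illness or any other cause, "they will continued to be followed on study until a progression event, death, or withdrawal from study". Section 8.6 asks for at least six months of endpoint follow-up for everyone, and Section 13.3 collects data to death or five years.

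**Forms.**
- Appendix O (Off-Study): "Complete this form if the patient has completed or is removed from the study". Its reasons include "Adverse Event/Side Effects/Complications" and "Enrolling Physician Decision". Refusal of follow-up, loss to follow-up, death and completed follow-up are separate boxes, and consent withdrawal is a separate question.
- Appendix M (Study Withdrawal): a single date field, "Date Study Treatment Stopped or Withdrawal". Its reasons include "Unanticipated Adverse Event/Serious Adverse Event" and radiotherapy that was started but not finished.
- Appendix F (30-day visit) asks "Was the subject removed from the study" and, if so, directs staff to the Off-Study form.
- Appendix Q (Off Treatment) already carries both the toxicity and the physician-decision reasons.

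**Analysis.** Section 8.10 ends PFS and OS at the event or last contact and names only loss to follow-up as censored. Section 14.1 has no censoring rule.

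**The concern.** Section 8.5 accepts withdrawal from study as an end of follow-up but does not define it. The forms allow toxicity, a physician's decision or unfinished radiotherapy to be recorded as that exit. A coordinator who treats an Appendix O or M entry as final could stop scans in a patient who has neither progressed nor refused.

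The treatments are not blinded, and one arm adds radiation. Removal for toxicity may therefore be more common in that arm, and unfinished radiotherapy can occur only there. If removed patients also have a worse prognosis, censoring them breaks the assumption behind the Kaplan-Meier, log-rank and Cox analyses, in the direction that flatters radiation. Even without that, PFS events are lost, and so are late-toxicity data that Section 14.2 plans to report.

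**Working it through.** **1. The texts side by side.** The two disputed Appendix O boxes cannot mean patient refusal or consent withdrawal, which that form records separately. They are not needed as treatment-stop codes, because Appendix Q holds both. What they add is an exit from the study that Section 8.5 does not provide for when immunotherapy is stopped. On Appendix M, the merged date means that stopping treatment cannot be told apart from leaving the study.

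**2. The plan's own figure.** Inputs from Section 13.1: 112 randomized 2:1, medians 8 and 15 months, two-sided alpha 0.05, power 0.80, 54 months' accrual and 60 months in total (so 6 months' minimum follow-up). Survival is assumed exponential and accrual uniform.

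- Event probability: p = 1 - [exp(-6λ) - exp(-60λ)]/(54λ), with λ = ln 2/median. Control 0.874, radiation 0.721.
- Expected events: 112 × (0.874/3 + 2 × 0.721/3) = 86.5.
- Power = Φ(√(D × 2/9) × |ln HR| - 1.96), with HR = 8/15 and |ln HR| = 0.6286. For D = 86.5: Φ(4.384 × 0.6286 - 1.96) = Φ(0.796) = 0.787.

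This is within two points of the stated 0.80. The increase from 112 to 125 (112/0.9 = 124.4) covers patients who progress before randomization. Section 13.1 states no allowance for loss after randomization.

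**3. Effect if removed patients are censored.** The documents give no removal rates, so these are assumptions. A simulation (75 against 37 patients, 4,000 runs per scenario) removed patients at a uniform time in the first 6 months. Their later hazard was multiplied by 1, 2 or 3. Censoring at removal was compared with full follow-up. The simulation starts the clock at time zero with the Section 13.1 medians and ignores the gap between first systemic therapy and randomization.

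| Removed, radiation/control | Events if censored | Formula power | HR, censored | HR, full follow-up (hazard ×1 / ×2 / ×3) |
|---|---|---|---|---|
| 0% / 0% | 86.5 | 0.787 | 0.530 | 0.530 |
| 5% / 5% | 82.9 | 0.770 | 0.525-0.531 | 0.528 / 0.529 / 0.537 |
| 10% / 5% | 80.8 | 0.759 | 0.525-0.526 | 0.525 / 0.545 / 0.555 |
| 15% / 5% | 78.5 | 0.747 | 0.528-0.531 | 0.528 / 0.563 / 0.580 |
| 20% / 5% | 76.3 | 0.735 | 0.525-0.530 | 0.528 / 0.577 / 0.600 |

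Events are for hazard ×1 and change by no more than about 0.2 otherwise. Formula power puts that count into the expression in step 2; for example, D = 76.3 gives Φ(4.118 × 0.6286 - 1.96) = Φ(0.628) = 0.735. In the three unequal-rate scenarios, simulated power with censoring was 0.76-0.79, against 0.80 with no removals.

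**4. Reading the bias.** With equal hazards there is no bias, only lost events. With equal 5% rates the HR hardly moves. With 20%/5% and double hazard, the shift in log HR is ln(0.577/0.530) = 0.085. The standard error is 1/√(76.3 × 2/9) = 0.243, so the shift is about 0.35 of a standard error. At triple hazard it is ln(0.600/0.525) = 0.134, about 0.55. In that last case the test rejects in 77% of runs with censoring but in 63% with full follow-up. With no direct effect of radiation, the same case shows an HR of 0.994 where full follow-up gives 1.089.

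**The case against.** A reader might infer that the plan already censors these patients at the off-study date, so that PFS and OS will be biased towards radiation. The documents do not support this. Section 8.10 names only loss to follow-up, Section 14.1 contains no censoring rule, Section 13.3 collects data to death or five years, and none of the forms cited here says that follow-up stops. A reason box records what happened; it does not override Section 8.5.

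Other limits also stand. Appendix M has no physician-decision option, and an entry there may mean only that treatment stopped. Its progression box causes no PFS censoring, because progression is the event, and Section 8.4.2 then keeps the patient in survival follow-up. Appendix F asks whether removal has occurred and does not prompt it. The Section 3.0 sentence concerns the radiation arm only. OS is better protected, because Appendix L accepts survival status from records, obituaries or family. Section 8.3 and Appendix N were not available in the text read here and might clarify the point. Finally, simply deleting reason boxes could hide why patients left.

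These points reduce the concern from an expected bias to a possible one. They do not remove the conflict: Section 8.5 lets an undefined withdrawal end follow-up, and the forms allow toxicity or unfinished radiotherapy to be recorded as one.

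**Conclusion.** The forms and the protocol text disagree on whether a patient who stops treatment for toxicity or by physician decision can leave the study. The conflict is certain; harm is conditional. Events are lost only if follow-up actually stops. The HR is biased only if, in addition, removed patients have a different hazard and removal rates differ by arm. The documents give no figures for any of these.

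Under assumed removal of 10-20% against 5%, 6 to 10 of about 86 PFS events are lost and formula power falls from 0.79 to 0.74-0.76. With two to three times the hazard after removal, an HR of 0.545-0.600 under full follow-up would be seen as about 0.53. That shift is well under one standard error. Severity is moderate to low; the repair is worth making because it is cheap and lost scans may not be recoverable.

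**What to change.** 1. Appendix O: limit off-study reasons to death, loss to follow-up, refusal of follow-up or withdrawal of consent, and completed follow-up.
2. Record toxicity and physician decision as treatment-stop reasons on Appendix Q, where both boxes already exist, so that the reason is kept.
3. Appendix M: replace the single date with a treatment-stop date and a consent-withdrawal date, and remove incomplete radiotherapy as a reason for study withdrawal. Item 2 of that form already captures it.
4. Sections 8.5 and 8.10: state that stopping any protocol treatment does not end imaging before progression or survival follow-up, and is not a reason for censoring.

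The cost is edits to two forms and a short statement in the protocol. No patients, visits or scans are added beyond those planned, and no rule on when treatment stops is changed.

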**Did the patient withdraw consent to participate in the study? Yes  No**

(If Yes, have the patient fill out the Withdrawal of Consent form)

**Appendix P: Protocol Deviation Form**

PID Number _____	DOB _____
Deviation Date: ____/____/____ (MM/DD/YYYY)	
Interval from date of day 1 of cycle 1 of chemo immunotherapy: _____ days	
Deviation	
 Patient does not meet inclusion/exclusion criteria: Specify reason for deviation.	
<hr/>	
 Patient did not sign informed consent prior to procedure: Specify reason for deviation.	
<hr/>	
 Missed visit: Specify reason for deviation.	
<hr/>	
 Visit not completed per protocol: Specify reason for deviation.	
<hr/>	
 Visit out of window: Specify reason for deviation.	
<hr/>	
 Missed test, exam: Specify reason for deviation	
<hr/>	
 Other, Specify	

**Appendix Q: Off Treatment**

Instructions: Fill out this form when a patient goes off treatment.	
Off Treatment:	
1. Off Treatment Date ____/____/____ (MM/DD/YYYY)	
2. Off Treatment Reason:	
 Adverse Event/Side Effects/Complications	
 Alternative Therapy	
 Cytogenetic resistance	
 Death on Study (if death fill out the Survival Form )	
 Disease progression before active treatment	
 Disease progression, relapse before active treatment	
 Enrolling Physician Decision	
 Lost to follow-up: Date of last contact ____/____/____ (MM/DD/YYYY)	
 No treatment, per protocol criteria	
 Patient off treatment for other complicating disease	
 Patient withdrawal or refusal after beginning protocol therapy	
 Patient withdrawal or refusal prior to beginning protocol therapy	
 Treatment completed per protocol criteria	
 Other	
3. Explain: _____	
Is the patient evaluable for response?	
 Yes	
 No	
 Not assessed	
If No or Not assessed, please explain: _____	

## Appendix R: Mandatory DSMC SAE Reporting Guidelines

Data and Safety Monitoring Committee (DSMC) Serious Adverse Event (SAE) Notification SOP	Date: 02/11/2021
---	-------------------------

### **Mandatory DSMC SAE Reporting Requirements in WISER**

This document describes reporting requirements of adverse events from **WFBCCC Investigator Initiated interventional trials to the Data and Safety Monitoring Committee (DSMC)**. A trial is considered a **WFBCCC Investigator Initiated interventional trial** if the following criteria are met:

- 1) The Principal Investigator (PI) of the trial is a member of a department at the Wake Forest University Baptist Medical Center.
- 2) WFBCCC is considered as the primary contributor to the design, implementation and/or monitoring of the trial.
- 3) The trial is designated as "Interventional" using the Clinical Research Categories definitions provided by the NCI in the Data Table 4 documentation.  
(<https://cancercenters.cancer.gov/GrantsFunding/DataGuide#dt4>)

There are two distinct types of WFBCCC Investigator Initiated interventional trials based on where patient enrollment occurs. These include:

- 1) Local WFBCCC Investigator Initiated interventional trials defined as trials where **all patients are enrolled from one of the WFBCCC sites**. These include the main outpatient Cancer Center clinics (located in Winston-Salem) as well as WFBCCC affiliate sites located in Bermuda Run (Davie Medical Center), Clemmons, Lexington, High Point, or Wilkesboro.
- 2) Multi-Center WFBCCC Investigator Initiated interventional trials defined as trials where patients are enrolled from other sites in addition to WFBCCC sites.

There are three types of trials that are included in this category:

- a. Trials sponsored by the NCI Community Oncology Research Program (NCORP) that are conducted at multiple sites where the PI is a member of a department at the Wake Forest University Baptist Medical Center.
- b. Trials sponsored by Industry that are conducted at multiple sites and the PI is a member of a department at the Wake Forest University Baptist Medical Center.
- c. Trials sponsored by WFBCCC that are conducted at multiple sites and the PI is a member of a department at the Wake Forest University Baptist Medical Center.

All Adverse Events (AEs) and Serious Adverse Events (SAEs) that occur on any patients enrolled on WFBCCC Investigator Initiated Interventional trials must be entered into the WISER system. The only exception to this requirement is for patients enrolled on NCORP trials at non- WFBCCC sites. AEs and SAEs for NCORP patients enrolled at WFBCCC sites must be entered into the WISER system. Once these AEs and SAEs are entered in WISER, certain actions must be taken regarding the reporting of specific Adverse Events to the DSMC.

All Adverse Events that occur during protocol intervention (defined below) and are coded as either 1) **unexpected grade 4, 2) unplanned inpatient hospitalization > 24 hours (regardless of grade)**, or **grade 5 (death)** must be reported to the DSMC using the SAE console in WISER.

A research nurse or clinical research coordinator when made aware that an adverse event meets one of the above criteria has occurred on a WFBCCC Investigator Initiated interventional trial, is responsible for informing a clinical member of the DSMC by phone (or in-person) about the adverse event. The nurse/coordinator should contact the treating physician prior to calling the DSMC clinical member to obtain all details of the SAE, as well as all associated

A Randomized Trial of Consolidative Immunotherapy with vs without Thoracic Radiotherapy and / or Stereotactic Body Radiation Therapy (SBRT) after First-line Systemic Therapy for Metastatic NSCLC  
Wake Forest Baptist Comprehensive Cancer Center  
WFBCCC # 62718

toxicities to be recorded along with the SAE. In addition, this nurse or coordinator is responsible for entering the adverse event information into the SAE console in WISER. Once the adverse event has been entered into the SAE console an email informing the entire DSMC will be generated.

**THESE REPORTING REQUIREMENTS APPLY TO any staff member on the study team for a WFBCCC Institutional Interventional trial. Ultimately, the protocol PI has the primary responsibility for AE identification, documentation, grading and assignment of attribution to the investigational agent/intervention. However, when an AE event as described above is observed, it is the responsibility of the person who observed the event to be sure that it is reported to the DSMC.**

**What is considered during protocol intervention?**

During protocol intervention is considered to be the time period while a patient is on study treatment or during the time period within 30 days of last study treatment (even if patient begins a new (non-study) treatment during the 30 days). This window of 30 days should be the standard window to be used in all protocols unless a specific scientific rationale is presented to suggest that a shorter window can be used to identify events. If it is a trial sponsored by Industry and the sponsor requires a longer window for monitoring of SAEs, then the longer window of time specified by the sponsor should be followed.

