  - c. The schedule above is standard of care for imaging followup. Should a patient be enrolled after starting maintenance immunotherapy and after their first 3 month followup scan, then they may be allowed to switch to 6 months interval imaging at 3yrs from the end of chemo-immunotherapy, rather than a full 3 yrs from the date of randomization in accordance with standard of care. At discretion of treating oncologist.
7. Definition of 1 mo. or 30 day followup
  - a. For patients randomized to RT, this time point is considered 30 days +/- 14 days from end of all radiation therapy treatments
  - b. For patients randomized to immunotherapy alone, this time point is considered 30 days +/- 14 days from the end of the 2nd cycle of on protocol maintenance immunotherapy
8. Two tubes of whole blood may be collected at time of registration or any time prior to initiating any protocol directed therapy and at the 1 month follow up +/- 2 weeks.
9. If patients progress and are not eligible for randomization, or if they progress at any point on the study, they are only followed w appendix L for survival after the point of progression

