### For patients randomized to radiation:

Patients will undergo CT imaging of chest/abdomen/pelvis at 1 month after the last treatment of radiation is completed. Subsequently, they will undergo CT imaging of chest/abdomen/pelvis every 3 months for 3 years, then every 6 months for 2 years per standard of care.

**For patients randomized to continue maintenance immunotherapy:** alone, they will undergo CT imaging of chest/abdomen/pelvis at 1 month after the 2nd cycle of protocol directed maintenance immunotherapy has been delivered. Subsequently, they will undergo CT imaging of chest/abdomen/pelvis every 3 months for 3 years, then every 6 months for 2 years per standard of care.

Should a patient be enrolled after starting maintenance immunotherapy and after their first 3 month followup scan, then they may be allowed to

switch to 6 months interval imaging at 3yrs from the end of chemo-immunotherapy, rather than a full 3 yrs from the date of randomization in accordance with standard of care. At discretion of treating oncologist.

If a patient, has suspicion of progression but requires closer interval followup than 3 months or additional imaging, this is allowable at the discretion of the treating physician. If ultimately, they are deemed to not have progressive disease, they would then resume the schedule listed in the study calendar above.

**8.4.2** Patients who progress on or after protocol directed therapy will be followed for survival only as per Appendix L without further protocol follow up requirements. This includes progression of the protocol treated tumors, non-protocol treated tumors and the development of new metastatic disease. Tumor progression will be determined by RECIST criteria.

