#### **8.6 Duration of Follow Up**

All patients should be followed for study endpoints for a minimum of six months. Afterwards patients without progression will be followed as listed in the study calendar.

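### Adverse events stay reportable for 30 days after the last study treatment, but no adverse-event contact is scheduled for the part of that window after progression

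*Combined protocol and SAP*

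**What the plan says.** Appendix R sets two duties. The first concerns data entry, in the WISER system: "All Adverse Events (AEs) and Serious Adverse Events (SAEs) that occur on any patients enrolled on WFBCCC Investigator Initiated Interventional trials must be entered". The second concerns DSMC notification of unexpected grade 4 events, unplanned admissions over 24 hours and deaths that occur during protocol intervention. That period covers therapy itself and also events "during the time period within 30 days of last study treatment (even if patient begins a new (non-study) treatment during the 30 days".

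Follow-up after progression is set elsewhere:

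- Section 8.4.2 gives the main rule: "Patients who progress on or after protocol directed therapy will be followed for survival only as per Appendix L without further protocol follow up requirements".
- Study calendar, footnote 9: "if they progress at any point on the study, they are only followed w appendix L for survival after the point of progression".
- Section 3.0, repeated in Appendix A, has a similar sentence in the text for the radiation arm.
- Section 8.6 is general: "All patients should be followed for study endpoints for a minimum of six months". Adverse-event frequency is one of the outcomes (5.2.3).

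Appendix L records vital status, dates and source, and nothing on adverse events. The 30-day form, Appendix F, does ask about adverse events in the preceding 30 days. For the radiation arm, however, "this time point is considered 30 days +/- 14 days from end of all radiation therapy treatments"; for the immunotherapy arm it follows the end of the second on-protocol cycle. Section 8.5 puts disease progression first among the reasons for ending treatment.

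**The concern.** The last dose and the switch to survival-only follow-up will often fall close together, because progression ends both treatment and scheduled assessment. Appendix R works by awareness: staff act once they learn of an event, and the 24-hour limit for entry runs from first knowledge. After progression no visit, call or form is scheduled that would bring a toxicity to their notice.

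What is at stake is how completely toxicity is captured in the plan's own safety window. The toxicity objective (2.2.3) depends on it. So does the rule in Section 13.4 to halt at half of accrual if 25% or more have grade 3 or higher pneumonitis. A grade 3 pneumonitis without an admission over 24 hours does not meet the DSMC notification criteria in Appendix R, so it is counted only if ordinary adverse-event collection picks it up.

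**Working it through.** The plan states no figure on this point. The check compares the texts and then gauges how much of the window, and how many patients, are affected.

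**1. What is scheduled inside the 30-day window**

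| Source | Tied to | Reaches day 30 after the last dose once the patient has progressed? |
|---|---|---|
| Section 6.0, CTCAE grading | each immunotherapy cycle | No, it ends with treatment |
| Section 8.1, toxicity row | 1-month, 3-monthly and 6-monthly visits | No, under 8.4.2 |
| Appendix F | end of radiation, or end of cycle 2 | Only if that date happens to fall there |
| Appendix L | survival follow-up | Continues, but has no adverse-event item |
| Appendix R | awareness of an event | The duty continues, but no contact is scheduled |

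**2. How much of the window falls after progression**

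Let U be the days from last dose to the finding of progression. The uncovered part is 30 - U. Cycles last 3 weeks (Section 6.1). Assuming U lies between 0 and 21 days, the uncovered part is 30 - 21 = 9 to 30 - 0 = 30 days. If U is uniform, the mean is 30 - 10.5 = 19.5 days, or 65% of the window. Section 6.0 lets patients delay doses by up to 3 weeks. In that case U could exceed 21 and the uncovered part would be shorter.

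**3. How many patients would stop for progression**

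Inputs from Section 13.1: median PFS of 8 months (control) and 15 months (radiation) from the first chemo-immunotherapy treatment, 112 randomized, 2:1 allocation. The medians agree with the stated hazard ratio: 8/15 = 0.533. Section 8.5 refers to a total of 2 years of maintenance. Assumptions: exponential PFS, randomization at month r = 3-6, and end of maintenance at month c = 24-30 from the start of systemic therapy.

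Share with a PFS event before maintenance ends = 1 - 2^(-(c - r)/median).

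| r, c | Control | Radiation | Overall (1/3, 2/3) |
|---|---|---|---|
| 6, 24 | 1 - 2^(-18/8) = 0.790 | 1 - 2^(-18/15) = 0.565 | 0.640 |
| 4, 27 | 1 - 2^(-23/8) = 0.864 | 1 - 2^(-23/15) = 0.655 | 0.724 |
| 3, 30 | 1 - 2^(-27/8) = 0.904 | 1 - 2^(-27/15) = 0.713 | 0.776 |

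These shares treat every PFS event as a progression and ignore earlier stops for other reasons. Both can be relaxed in the middle row (23 months):

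- Let 14-35% stop for other reasons over the 23 months. The 14% is the adverse-event discontinuation rate quoted in Section 1.5 for the non-squamous trial; 35% is assumed. With g = -ln(1 - q)/23 and L = ln 2/median, the share is L/(L + g) x (1 - exp(-23(L + g))). Overall this gives 0.684 at q = 0.14 and 0.618 at q = 0.35.
- Let 75-85% of PFS events be progressions (assumed). Then 0.684 x 0.85 = 0.581 and 0.618 x 0.75 = 0.463.

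The range is therefore about 46% to 78%, or 0.463 x 112 = 52 to 0.776 x 112 = 87 patients.

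**4. Patients who stop for toxicity, choice or completion**

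They stay on 3-monthly visits with a window of +/- 8 weeks (Sections 8.1 and 8.4.1). The tolerance alone is 8 x 7 = 56 days, longer than the 30-day window. No contact by day 30 is assured for them either.

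**5. A radiation patient who progresses at the 1-month CT**

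Take the CT at day 30 after radiation. If immunotherapy has not resumed, radiation is the last study treatment and Appendix F falls at the end of the window, so little is lost. If a dose was given d days after radiation, the window closes at day d + 30 and d days lie after progression; with d = 21, for illustration, that is 21 days.

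**The case against.** The strongest reply is that the provisions govern different things and can be obeyed together. Section 8.4.2 limits scheduled follow-up, while Appendix R governs entry and reporting, does not stop at progression and expressly continues when new treatment starts. That is right. A reader might infer that the two give opposite instructions, or that nobody is required to look for events. The text supports neither reading: Appendix R makes the protocol PI primarily responsible for identifying adverse events and adds that "it is the responsibility of the person who observed the event to be sure that it is reported to the DSMC". Section 8.6 can also be read as keeping all patients under endpoint follow-up for six months, though it is not reconciled with 8.4.2.

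Other limits also stand:

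- Grading at each cycle, and at the visit where progression is found, can cover the early part of the window.
- In the calendar, footnote 9 is attached only to the row for Appendices G, J and L, so Section 8.4.2 carries most of the weight.
- A reader might fear that a toxic death would be missed. Appendix L records death and its date, and Appendix R makes a death inside the window reportable. Late reporting or poor attribution is possible; non-detection is not shown.
- Section 14.2 plans only descriptive toxicity summaries. The larger expected loss among controls (79-90% with a PFS event before maintenance ends, against 57-71%) is therefore a secondary matter.

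These points narrow the gap without closing it. A duty that starts with awareness still needs some contact that creates awareness.

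**Conclusion.** The concern holds in a limited form. The reporting duty runs to day 30 after the last study treatment, but scheduled ascertainment stops at progression, and no form is anchored to the last dose for any patient. Roughly half or more of randomized patients would stop for progression. An unqualified claim that most patients are affected goes too far: the lower end of the range is below one half, and the upper end counts deaths as progressions and allows no other reason for stopping. The 9-30 uncovered days rest on the assumed 0-21 day interval. The documents do not give the timing of stops, the reasons for them, or the mix of progression and death, so these figures indicate scale only.

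**What to change.** In Section 8.4.2, footnote 9 and the matching sentence in Section 3.0 and Appendix A, add an exception: adverse events and SAEs continue to be collected and reported until 30 days after the last study treatment, regardless of progression or new therapy. Have Appendix F completed once more in both arms, by telephone or record review, 30 days after the last study treatment. This also covers patients who stop for toxicity, choice or completion. Align Section 8.6 by stating which endpoints its six-month minimum covers and how it applies after progression.

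The cost is amendment wording and one extra telephone or chart check per patient, using an existing form. No procedure is added and no treatment rule changes.
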